A confirmed diagnosis of organ transplant rejection will be based on histologic assessment or tissue biopsy. The investigator must review results of safety laboratory assessments as soon as they are available. The schedule of sampling for safety laboratory assessments is presented in the applicable SoE.

Vital sign measurements will include systolic and diastolic blood pressure, heart rate, respiratory rate, and body temperature (preferred route is oral). The participant will be seated for at least 5 minutes before all measurements are taken. Vital signs will be measured at the time points indicated in the applicable SoE. At dosing visits, vital sign measurements will be collected once before injection and at least 30 minutes after injection (before participants are discharged from the study site).

Physical examinations will be conducted according to the applicable SoE. A full physical examination will be performed at Day 1 and symptom-directed physical examinations will be performed at other time points.

Immunogenicity Assessments:

Blood samples for immunogenicity assessments will be collected at the time points indicated in the applicable SoE. The following analytes will be measured:

- Serum nAb level against SARS-CoV-2 as measured by pseudovirus and/or live virus neutralization assays

- Serum binding antibody (bAb) against SARS-CoV-2 S protein measured by ligand binding assay specific to the SARS-CoV-2 S protein

Assessments for SARS-CoV-2 Infection

Study participants will have NP samples collected for SARS-CoV-2 testing by RT-PCR at time points specified in the applicable SoE. A study illness visit or a consultation will be arranged within 72 hours or as soon as possible to collect an NP or nasal swab sample (NP is preferred) to ascertain the presence of SARS-CoV-2 via RT-PCR if a participant experiences any of the following:

- Signs or symptoms of SARS-CoV-2 infection as defined by the US Centers for Disease Control and Prevention
- Close contact exposure to an individual confirmed to be infected with SARS-CoV-2
- MAAE suggesting a SARS-CoV-2 infection

If the participant had known close contact exposure to COVID-19 (eg, close contact exposure to someone with confirmed COVID-19), it will be captured in the COVID-19 exposure form.

If scheduled, the study illness visit may collect additional clinical information at the investigator's discretion, including but not limited to medical history, physical examination, blood sampling for clinical laboratory testing, and nasal, saliva, and/or NP swab sampling for viral PCR (including multiplex PCR for respiratory viruses, including SARS-CoV-2) to evaluate the severity of the clinical case. Radiologic imaging studies may be conducted. During this visit, a blood sample will also be collected for immunologic assessment of SARS-CoV-2. All findings will be recorded in the eCRF.

If participants are confirmed to have SARS-CoV-2 infection, the investigator will notify the participant and the participant's primary care physician of the diagnosis. If the study participant does not have a primary care physician, the investigator will assist them in obtaining one. The participant will also be instructed on infection prevention measures consistent with local public health guidance.

Any confirmed symptomatic SARS-CoV-2 infection occurring in participants will be captured as an MAAE along with relevant concomitant medications and details about severity, seriousness, and outcome. Additionally, a convalescent visit will be scheduled approximately 28 days (+7 days) after diagnosis. At this visit, an NP swab sampling for viral PCR and a blood sample will be collected for potential immunologic assessment of SARS-CoV-2 infection.

Exploratory Assessments:

Qualitative and quantitative measures of viral load of SARS-CoV-2 will be assessed by RT-PCR material from NP swab samples obtained at illness visits. Any SARS-CoV-2 genetic sequencing will be performed on the same samples.

In Part A, cellular immune response (eg, markers of CMI, T-cells, and B-cells) will be assessed on Day 1 before vaccination and at Days 36 and Day 92 in a subset of up to 50 unvaccinated participants who receive 3 doses of vaccine in the SOT group (kidney or liver) (Group A2); from 20 unvaccinated healthy study participants (Group A5) (Day 1 before vaccination and Day 36); and from a subset of at least 50 previously vaccinated SOT recipients who receive dose 3 (Group A3) (Day 1 before vaccination and Day 8). In Part B Booster Phase, CMI will also be assessed on BD-D1 before vaccination and BD-D8 from all participants in Part B. In Part B Booster Phase, blood sample will be collected for future biomarker analysis.

Statistical Methods:

Sample Size:

The planned sample size of approximately 240 participants (220 unvaccinated or previously vaccinated participants who have had a kidney or liver transplant and 20 unvaccinated healthy participants) who receive 2-dose regimen or 3-dose regimen of 100 µg of mRNA-1273, or 100 µg BD regimen are expected to provide useful estimates of Ab response at Day 29 for previously vaccinated SOT recipients who receive dose 3 in Part A, Day 113 for unvaccinated SOT recipients who receive the 3-dose regimen, at Day 57 for unvaccinated participants who receive the 2-dose regimen, and at BD-D29 (participants who receive a BD) (primary endpoints), respectively, for comparison to results from Study P301 (if available at the time of database lock). The healthy adult participants will be used primarily as a biological control for the CMI analysis. This study is designed for estimation purposes, and no between-group comparisons are planned.

Analysis Sets:

The analysis sets are defined in the following table:

Analysis Set	Description
Full Analysis Set (FAS)	All participants who received at least 1 dose of vaccine.
Modified Intent-to-Treat Set (mITT)	All participants who have negative SARS-CoV-2 status at baseline, defined as who have a negative RT-PCR test for SARS-CoV-2 and a negative serology test based on bAb specific to SARS-CoV-2 nucleocapsid protein (as measured by Roche Elecsys Anti-SARS-CoV-2 assay) at baseline.

Per-Protocol (PP) Subset	All participants in the mITT set who receive all planned doses of study vaccination per schedule and have no major protocol deviations that impact key or critical data.
PP Immunogenicity Subset	All participants who received planned doses of study vaccination per schedule, complied with immunogenicity testing schedule, and have no major protocol deviations that impact key or critical data. Participants who are seropositive at baseline will be excluded from the PP Immunogenicity Subset. The PP Immunogenicity Subset will be used for analyses of immunogenicity unless specified otherwise. The PP Immunogenicity Set will serve as the primary population for the analysis of SARS-CoV-2-specific bAb and nAb immunogenicity data.
Solicited Safety Set	All participant in the FAS who contributed any solicited AR data. The Solicited Safety Set will be used for the analyses of solicited ARs.
Safety Set	All participants who received at least 1 dose of vaccine. The Safety Set will be used for all analyses of safety except for the solicited ARs.

Abbreviations: AR = adverse reaction; bAb = binding antibody; nAb = neutralizing antibody; RT-PCR = reverse transcriptase polymerase chain reaction; SARS-CoV-2 = Severe Acute Respiratory Syndrome coronavirus 2; vaccine = investigational product.

Safety Analyses:

Given that the study does not have a concurrent unvaccinated SOT control group, descriptive statistics will be used to present safety data, and no comparisons with the healthy adult participants will be made.

All safety analyses will be based on the Safety Set, except summaries of solicited ARs, which will be based on the Solicited Safety Set. All safety analyses will be summarized by cohort and subcohort arm.

Safety and reactogenicity will be assessed by clinical review of all relevant parameters, including solicited ARs (local and systemic events), unsolicited AEs, MAAEs, SAEs, AESIs, AEs leading to discontinuation from dosing and/or study participation (withdrawal), biopsy-proven organ rejection, safety laboratory assessments, vital sign measurements, and physical examination findings.

The number and percentage of participants with any solicited local AR, with any solicited systemic AR, and with any solicited AR during the 7-day Follow-up Period after each dose will be summarized.

The number and percentage of participants with unsolicited AEs, SAEs, AESIs, MAAEs, Grade 3 or higher ARs and AEs, AEs leading to discontinuation from dosing and/or study participation (withdrawal), and biopsy-proven organ rejection will be summarized. Unsolicited AEs will be presented by Medical Dictionary for Regulatory Activities preferred term and system organ class.

The number of events of solicited ARs, unsolicited AEs/SAEs, AESIs, MAAEs, and adjudicated biopsy-proven organ rejection will be reported in summary tables.

Clinical laboratory data will be summarized by severity for each visit and as the maximum over all postvaccination visits. Graphical presentations may include box plots and shift plots. Evaluation of clinically significant changes in safety laboratory measurements will be considered independent of the toxicity grading scale.

For all other safety parameters, descriptive summary statistics will be provided. Further details will be described in the statistical analysis plan (SAP).

Immunogenicity Analyses:

The SAP will describe the complete set of immunogenicity analyses. The PP Immunogenicity Subset is the primary analysis set for immunogenicity unless otherwise specified. In Part A, the primary immunogenicity objective of this study is to evaluate serum Ab responses obtained 28 days after the second or third injection of 100 µg mRNA-1273 (Day 57 in unvaccinated

participants who receive 2 doses, Day 113 for unvaccinated SOT recipients who receive 3 doses, and Day 29 for previously vaccinated SOT recipients who receive dose 3). In Part B, the primary immunogenicity objective of this study is to evaluate serum Ab responses obtained 28 days after the BD. The results of the study will be described and evaluated against the Ab responses of adult healthy participants in this study and Study P301 (if available at the time of database lock).

Using the Ab threshold established from Study P301 (if available at the time of database lock), an additional exploratory analysis will be performed by measuring the proportion of participants with a serum Ab level at Day 57 (unvaccinated participants who receive 2 doses), Day 113 (unvaccinated SOT recipients who receive 3 doses), and Day 29 (previously vaccinated SOT recipients who receive dose 3) in Part A, and at BD-D29 (participants who receive a BD) greater than or equal to the Ab threshold of protection against COVID-19, with a 2 sided 95% CI using the Clopper Pearson method by cohort arm.

The GM level of serum Ab with corresponding 95% CI will be provided at each time point by cohort arm. The 95% CIs will be calculated based on the t-distribution of the log transformed values then back transformed to the original scale for presentation. Additionally, the proportion of participants with a 2 \times , 3 \times , and 4 \times rise in GM level from Day 1 will be measured.

All nAb and bAb endpoints will be summarized at each time point with Day 29 (previously vaccinated SOT recipients who receive dose 3) and Day 57 and Day 113(unvaccinated participants), and at BD-D29 (participants who receive a BD) as the time points of interest. The GM levels and GM fold rise of both nAb and bAb will be provided with corresponding 95% CIs. Reverse cumulative distribution curves for antibody titers for all time points will be presented.

Incident Cases of COVID-19 After Vaccination:

The number and percentage of participants with COVID-19 after vaccination in the SOT recipient and healthy cohorts will be provided. The number and percentage of participants with severe COVID-19 will be provided similarly.

For serologically confirmed SARS-CoV-2 infection or COVID-19, regardless of symptomatology or severity, infection rate will be provided by the healthy cohort arm.

As an additional analysis, the number and percentage of participants with symptomatic and asymptomatic COVID-19 or SARS-CoV-2 infection throughout the study will be summarized.

Study Analyses:

Interim Analyses:

An interim analysis of safety and immunogenicity data is planned after Day 57 (28 days after the second dose for unvaccinated participants), after Day 29 (28 days after dose 3 in previously vaccinated SOT recipients) in Part A, and at BD-D29 (28 days after BD in participants who receive a BD) in Part B; a clinical study report (CSR) will be prepared. An analysis of safety and/or immunogenicity may be performed at the Sponsor's discretion based on the availability of data.

Final Analysis:

The final analysis of all endpoints will be performed after all participants have completed all planned study procedures. Results of this analysis will be presented in a final CSR, including individual listings.

Additional information about all study analyses may be provided the SAP.

TABLE OF CONTENTS

CLINICAL STUDY PROTOCOL	1
PROTOCOL APPROVAL – SPONSOR SIGNATORY	2
DECLARATION OF INVESTIGATOR.....	3
PROTOCOL AMENDMENT SUMMARY OF CHANGES.....	4
PROTOCOL SYNOPSIS	9
TABLE OF CONTENTS.....	49
LIST OF TABLES.....	54
LIST OF FIGURES	54
LIST OF ABBREVIATIONS AND TERMS.....	55
1. INTRODUCTION	58
1.1. Study Rationale.....	58
1.2. Background and Overview	60
1.2.1. Nonclinical Studies.....	60
1.2.2. Clinical Studies.....	61
1.3. Benefit/Risk Assessment	66
1.3.1. Potential Benefits from Participation.....	66
1.3.2. Risks to Study Participants and Risk Mitigation	66
1.3.3. Overall Benefit/Risk Conclusion.....	68
2. OBJECTIVES AND ENDPOINTS	69
3. STUDY DESIGN	81
3.1. General Design	81
3.1.1. Study Periods	92
3.2. Scientific Rationale for Study Design	97
3.3. Justification for Dose and Choice of Study Population.....	99
3.4. End of Study Definition.....	100
4. STUDY POPULATION.....	101
4.1. Eligibility Criteria (Part A)	101
4.1.1. Eligibility Criteria for Transplant Recipients (Group A1, Group A2, and Group A3).....	101
4.1.2. Eligibility Criteria for Healthy Adults (Group A5)	103

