
 To describe the incidence of asymptomatic SARS-CoV-2 infection after mRNA-1273 vaccination in adult solid organ transplant (SOT) recipients and healthy adult participants with negative SARS-CoV-2 at baseline 	
 The incidence of asymptomatic SARS-CoV-2 infection among recipients of mRNA-1273 SARS-CoV-2 vaccine will be defined in participants with negative SARS-CoV-2 at baseline as bAb levels against SARS-CoV-2 nucleocapsid protein negative (as measured by Roche Elecsys) at Day 1, that becomes positive (as measured by Roche Elecsys) counted starting 28 days after the second dose and 28 days after the third dose of vaccine, OR Positive reverse transcriptase polymerase chain reaction (RT-PCR) counted starting 14 days after the second and after the third dose of vaccine 	

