
 To describe the incidence of asymptomatic SARS-CoV-2 infection after mRNA-1273 vaccination in adult solid organ transplant (SOT) recipients and healthy adult participants with negative SARS-CoV-2 at baseline 	
 The incidence of asymptomatic SARS-CoV-2 infection among recipients of mRNA-1273 SARS-CoV-2 vaccine will be defined in participants with negative SARS-CoV-2 at baseline as bAb levels against SARS-CoV-2 nucleocapsid protein negative (as measured by Roche Elecsys) at Day 1 that become positive (as measured by Roche Elecsys) counted starting 28 days after the second dose and 28 days after the third dose of vaccine, OR Positive reverse transcriptase polymerase chain reaction (RT-PCR) counted starting 14 days after the second and after the third dose of vaccine

 To describe the incidence of coronavirus disease 2019 (COVID-19) after vaccination with mRNA-1273 in SOT recipients and healthy participants 	
 First occurrence of COVID-19 starting 14 days after the second dose and after the third dose of vaccine, where COVID-19 is defined as symptomatic disease based on the following criteria The participant must have experienced at least TWO of the following symptoms: fever ($\geq 38^{\circ}\text{C}/\geq 100.4^{\circ}\text{F}$), chills, myalgia, headache, sore throat, or new olfactory and taste disorder(s), OR The participant must have experienced at least ONE of the following respiratory signs/symptoms: cough, shortness of breath or difficulty breathing, OR clinical or

Objectives	Endpoints

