8.3.4. Incident Cases of COVID-19 After Vaccination

The number and percentage of participants with COVID-19 after vaccination in the SOT recipient and healthy comparison cohorts will be provided. The number and percentage of participants with severe COVID-19 will be provided similarly.

For serologically confirmed SARS-CoV-2 infection or COVID-19, regardless of symptomatology or severity, infection rate will be provided by the healthy cohort arm.

As an additional analysis, the number and percentage of participants with symptomatic and asymptomatic COVID-19 or SARS-CoV-2 infection throughout the study will be summarized.

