## **6.5. COVID-19 and SARS-CoV-2 Infection Analysis**

For both Part A and Part B, the mITT Set (Part A/Part B) will be used for the analysis of COVID-19 and SARS-CoV-2 infection starting from 14 days after the second dose and third dose received for each participant group. The PP Set (Part A/Part B) may be used in the analyses as appropriate, unless otherwise specified.

**Baseline SARS-CoV-2 status and Pre-booster SARS-CoV-2 Status** is described in [Section 6.1](#). The serology test results based on Roche Elecsys assay at baseline, and the RT-PCR test results at baseline will be summarized by participant group.

Participants with pre-vaccination baseline positive or missing SARS-CoV-2 status will be excluded from the mITT Set (Part A) infection analysis.

Participants with pre-booster positive or missing SARS-CoV-2 status will be excluded from the mITT Set (Part B) infection analysis.

The post-baseline serology test results based on the Roche Elecsys assay and the RT-PCR test results will also be summarized by visit.

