### 6.5.2. Analysis of Infection Rates

For Part A and Part B, the number and percentage of subjects experiencing each of the infection events below will be summarized by participant group for the mITT Set:

- SARS-CoV-2 infection
- Asymptomatic SARS-CoV-2
- COVID-19
- Severe COVID-19
- Secondary case definition of COVID-19

For each of these summaries, the incidence rate (i.e. the infection rate) will be provided by participant group, calculated as the number of cases divided by the total person-time. The 95% CI of the incidence rate will be calculated using the exact method (Poisson distribution) and adjusted by person-time.

Person-time is defined as the total time from first dose of each part of the study (Part A or Part B) to the earliest of the following dates: date of event, dose date in next part, last date of study participation, censoring time, or efficacy data cutoff date.

For participants who are a case for symptomatic COVID-19, symptoms reported by these participants will be summarized.

For SARS-CoV-2 infection, asymptomatic SARS-CoV-2 infection, COVID-19, and severe COVID-19, the timeframe for the counting cases will begin at 14 days after the last planned dose and will differ by study arm:

- 2-dose unvaccinated without booster: from day 43 up to and including day 394,
- 3-dose unvaccinated without booster: from day 99 up to and including day 450,
- 3-dose previously vaccinated with Moderna COVID-19 vaccine without booster: from day 15 up to and including day 365.
- 2-dose unvaccinated with booster: from BD-Day 1 + 14 up to and including BD-Day 181.

Confidential

- 3-dose unvaccinated with booster: from BD-Day 1 + 14 up to and including BD-Day 181)
- 3-dose previously vaccinated with Moderna COVID-19 vaccine with booster: from BD-Day 1+ 14 up to and including BD-Day 181 .
- 3-dose previously vaccinated with mRNA or non-mRNA COVID-19 vaccine with booster: from BD-Day 1 + 14 up to and including BD-Day 181.

In addition, the COVID-19 and SARS-CoV-2 infection endpoints may be also analyzed by specimen types (i.e. NP swab, nasal swab, or saliva samples), calendar months, time periods, and all types of the diagnostic test (i.e., both RT-PCR results and other COVID-19 test results). The number and percentage of subjects experiencing COVID-19 may be summarized by specific variant groups. Listings of serum nAb and bAb levels against SARS-CoV-2, solicited ARs and unsolicited AEs will be provided for subjects infected by SARS-CoV-2.

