## **7. Changes from Planned Analyses in Protocol**

Not applicable.

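### COVID-19 and severe COVID-19 are summarised only in participants negative at baseline or before the booster, although the objective carries no such condition; add a Full Analysis/Safety Set summary beside the mITT one

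*Protocol*

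**What the plan says.** **Objective.** Protocol Table 1 (Section 2) states the COVID-19 objective as "To describe the incidence of coronavirus disease 2019 (COVID-19) after vaccination with mRNA-1273 in SOT recipients and healthy participants". Severe COVID-19 is an endpoint under the same objective. The asymptomatic-infection objective next to it is limited to transplant recipients and "healthy adult participants with negative SARS-CoV-2 at baseline". Section 7.3 follows the same pattern: serologic infection requires a negative baseline, while the symptomatic and severe case definitions do not.

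**Protocol analysis text.** The synopsis says "The number and percentage of participants with COVID-19 after vaccination in the SOT recipient and healthy cohorts will be provided". Section 8.3.4 says nearly the same and adds "The number and percentage of participants with severe COVID-19 will be provided similarly". It also promises that participants with "symptomatic and asymptomatic COVID-19 or SARS-CoV-2 infection throughout the study will be summarized". No analysis set is named for any of these. Table 5 (Section 8.2) defines an mITT Set of baseline-negative participants and gives it no stated use.

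**SAP.** Sections 2.2 and 2.3 repeat the unrestricted objective. Section 6.5 then assigns the mITT Sets to all COVID-19 and infection analyses: "Participants with pre-vaccination baseline positive or missing SARS-CoV-2 status will be excluded from the mITT Set (Part A) infection analysis". A matching sentence covers pre-booster status in Part B. Section 6.5.2 lists five infection events, among them COVID-19, severe COVID-19 and the secondary case definition, which "will be summarized by participant group for the mITT Set". The PP Sets may also be used. Section 7, on changes from the protocol, reads "Not applicable".

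**The concern.** A negative baseline is needed to recognise a new seroconversion, so mITT suits asymptomatic and serology-defined infection. Symptomatic disease with a positive RT-PCR, counted from 14 days after dosing, does not depend on it in the same way, and the protocol's wording draws that line. With mITT as the only population, the SAP answers a narrower question than the stated objective.

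At stake are a few cases in a small cohort. A transplant recipient with positive or missing status who develops severe COVID-19 would add nothing to the severe COVID-19 count or rate. If people with prior infection have a lower risk, the mITT percentage would also sit above that of the enrolled cohort.

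**Working it through.** The plan gives no figure to reproduce, so the main check compares texts and analysis sets.

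1. **Who the objective covers.** Transplant recipients and healthy participants, with no condition on status (Protocol Table 1; SAP 2.2 and 2.3).
2. **Who the SAP counts.** The mITT Set requires negative status at baseline for Part A (SAP 5.2.1) and before the booster for Part B (5.3.1). Section 6.5 excludes positive and missing status in each part.
3. **Whether another set brings them back.** PP is drawn from mITT (SAP 5.2.2, 5.3.2). No Full Analysis/Safety Set summary of COVID-19 is specified. The number of endpoint cases from excluded participants is therefore zero by construction.
4. **Whether such participants exist.** Protocol 3.1 lets nucleocapsid-positive participants continue. Known prior infection or a previous positive test excludes entry to Part A (4.1.1.2 and 4.1.2.2, criterion 1) and, through 4.2.2, to Group B4. At those entry points only undetected infection or missing status remains. For Part A participants moving to Part B, 4.2.1 sets no infection condition, and footnote 1 of Table 10 allows a convalescent participant who is no longer symptomatic to be boosted. SAP 6.1 classes any positive RT-PCR or serology on or before BD-Day 1 as pre-booster positive, so these participants leave the Part B infection analysis.
5. **Other outputs.** The protocol's summary over the whole study has no explicit SAP counterpart; 6.5.2 counts from 14 days after the last planned dose. The listings for infected participants (6.5.2) and the optional clinical-profile summaries (6.6) concern SARS-CoV-2 infection, which 6.5.1.1 defines in baseline-negative participants.

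**Illustration only.** The documents give no share positive or missing (f), no risk in baseline-negative participants (p) and no relative risk in those excluded (RR). Assume f = 5–20%, p = 5–20% and RR = 0.2–1.0, with N = 220, the total planned number of transplant recipients, which the documents do not split by part.

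- Participants excluded = N × f: 220 × 0.05 = 11 to 220 × 0.20 = 44.
- Uncounted cases = N × f × p × RR: 220 × 0.05 × 0.05 × 0.2 = 0.11 to 220 × 0.20 × 0.20 × 1.0 = 8.8.
- Whole-cohort incidence = p × [(1 − f) + f × RR]. With p = 20% and RR = 0.2 it is 0.20 × (0.95 + 0.01) = 19.2% at f = 5%, and 0.20 × (0.80 + 0.04) = 16.8% at f = 20%, against 20.0% in mITT.
- With RR = 1 the percentage is unchanged and only the count falls.

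**The case against.** **This is not a clear contradiction of the protocol.** Section 8.3.4 names no analysis set, Section 8 leaves detail to the SAP, and Table 5 defines mITT and PP without assigning them a use. Infection endpoints are a natural use for them. This stands. A reader might infer that the SAP overrode the protocol and hid a change; the documents do not support that. They support only that the objective's wording and the analysis set are not aligned, and that this is not noted.

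**The cases are not lost.** Confirmed COVID-19 is recorded as a medically attended adverse event (Protocol 7.3.1) and tabulated in the Safety Set, which has no status restriction. SAP 6.1 lists baseline status, positive or negative, as a safety subgroup, and 6.3.1.1 presents the adverse event overview by it. This also stands, but those tables apply no COVID-19 case definition, no 14-day rule and no person-time, and the subgroup has no missing category. They do not give the incidence that the objective asks for.

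**Part B carries less weight.** Its COVID-19 endpoint is exploratory, and a baseline-negative participant with a qualifying Part A case is already counted there. A positive RT-PCR in someone recently convalescent may be residual rather than new. SAP 6.1 also treats an unavailable BD-Day 1 RT-PCR with negative serology as negative, which shrinks the missing group, although 5.3.1 is worded differently. All of this is fair. It argues for showing results by status, and for keeping mITT.

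**No primary conclusion depends on it.** The study is descriptive, with no formal hypothesis testing. That is correct.

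**Conclusion.** The point holds as a gap between the stated objective and the only analysis population. As the SAP stands, no COVID-19 incidence summary includes a symptomatic case from a participant with positive or missing status.

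Its size cannot be computed from the documents. The effect is probably small in Part A and Group B4, because known prior infection is excluded. It may be larger among Part A participants infected on study and then boosted. The illustrative counts rest wholly on assumed inputs.

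Two further readings go too far. One is that the mITT rate overstates cohort incidence by some definite percentage. That needs a positivity share and a protective effect that the documents do not give, and an effect of prior infection would not apply to participants whose status is merely missing. The other is that mITT is the wrong set and should be replaced. It is a defensible analysis; the problem is that it is the only one. Which of the two leads is a matter of preference.

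**What to change.** In SAP 6.5 and 6.5.2:

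- Keep the mITT analysis. For each part, add a Full Analysis/Safety Set summary of COVID-19, severe COVID-19 and the secondary case definition, overall and by baseline or pre-booster status (negative, positive, missing). Settle one definition of missing pre-booster status, since 5.3.1 and 6.1 differ.
- Keep mITT alone for asymptomatic and serology-defined infection.
- Run the protocol's whole-study summary of symptomatic cases on the same full set.
- List the use of mITT for COVID-19 in SAP Section 7.

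The cost is a few extra tables and no new data. The full-set rate mixes previously infected and uninfected participants, and may include residual RT-PCR positivity in convalescent participants. The split by status makes that visible.
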